**12.12 \* Will samples be coded?**

Yes  No

If Yes, Please describe coding scheme consistent with GCP. If samples will not be coded, please provide justification for this proposed departure from GCP practice.

The blood samples for all volunteers will be coded using the IRB approval number, date, and subject number, e.g. TWA-0804-001. The subject codes will be maintained in a password-protected database

on a RUH backed-up computer in the [name] lab that is accessed only by the Principal Investigator and the research team.

Once the samples are processed, the plasma will be stored in a -80C freezer in the [name] lab until time of assay.

If available, upload the Data and Sample Sharing Management Plan approved by RU IT.

Version	Title	Category	Expiration Date	Document Outcome	Checked Out	View Document
---------	-------	----------	-----------------	------------------	-------------	---------------

No Document(s) have been attached to this form.

## 13.0

### Participants of Study

#### 13.1 Specify age range of participants:

\* Minimum Age:

18

\* Maximum Age:

80

Please note: If the age of participants indicated is less than 18 years old, you will be prompted to attach a Pediatric Assent form later on in the submission process. A link to the Pediatric Assent form can be found in the Help link to the right, or this form can be downloaded later on in the submission process.

#### 13.2 \* Indicate the gender(s) of the participants:

- Female
- Male
- Unknown
- Not Reported

#### 13.3 \* Indicate projected enrollment by race and ethnicity. See Help for disease/volunteer population demographics.

Ethnic Category	Sex/Gender			
	Females	Males	Unknown or Not Reported	Total
Hispanic or Latino	31	28	0	59
Not Hispanic or Latino	82	74	0	156
Unknown (individuals not reporting ethnicity)	0	0	0	0
Ethnic Category: Total of All Subjects*	113	102	0	215
Racial Categories				
American Indian/Alaska Native	0	0	0	0

Asian	14	12	0	26
Native Hawaiian or Other Pacific Islander	0	0	0	0
Black or African American	38	33	0	71
White	61	57	0	118
More Than One Race	0	0	0	0
Unknown or Not Reported	0	0	0	0
Racial Categories: Total of All Subjects*	113	102	0	215

#### **13.4 Exclusion of Protected Groups:**

**\*Research involving human participants should be designed/conducted to be as broadly inclusive as possible regarding sex, gender, race, age, and ethnicity. Exclusions regarding these characteristics require an explanation of the rationale and justification.**

**Will participants of a specific sex/gender/race/ethnicity/age or other protected group characteristic be excluded from participation?**

Yes  No

#### **13.5 Vulnerable Populations**

Indicate whether any of the following populations will be included in the study:

- Children
- Pregnant Women
- Cognitively Impaired Persons
- RU Employees
- RU Students
- Other:

If you checked any of the above, give a brief explanation of the need to use these particular individuals:

RU employees and students will be enrolled if they meet study eligibility. Special precautions will be used in recruiting employees and students of the Rockefeller University to minimize the possibility of undue influence. Rockefeller University employees will be made aware of the study through flyers rather than directed presentations to selected groups. Subjects will be reassured that refusal to participate in the study will not affect their studies or employment in any way and that all medical records will be kept in accordance with HIPAA guidelines to ensure privacy.

If the participant is a Rockefeller University employee, does she/he work within the Laboratory of the Principal Investigator or Co-Investigator(s)?

- Yes
- No
- N/A

If the participant is a Rockefeller University student, does she/he work within the Laboratory of the Principal Investigator or Co-Investigator(s)?

- Yes
- No

N/A

**13.6 \*What is the total number of evaluable participants you plan to enroll at Rockefeller University Hospital over the course of the entire study?**

215

**13.7 \* What is the total number of participants who will need to sign consent at *Rockefeller University Hospital* over the course of the entire study to result in the desired number of evaluable participants?**

278

**13.8 \* What is the total number of participants you plan to sign consent at *Rockefeller University Hospital* in the next year?**

20

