**215 volunteers who meet all the eligibility criteria will be enrolled in this study.**

The study is divided into 3 arms. The groups are defined as follows:

**Arm I: Age 18-64 group:** Groups of 10 study participants each (except for group 2 which includes 25 participants) < 65 years of age (< 50 years of age for Flumist vaccine and < 55 years of age for meningococcal vaccines) will be **vaccinated with one of seven FDA approved vaccines (85 participants total):** **Group 1)** Fluzone intradermal influenza virus vaccine, **Group 2)** Fluzone intramuscular influenza virus vaccine, **Group 3)** Pneumovax 23 (plain polysaccharide pneumococcal vaccine), **Group 4)** Prevnar/PCV13 (pneumococcal conjugate vaccine), **Group 5)** MPSV4 (plain polysaccharide meningococcal vaccine), **Group 6)** Mencevo (meningococcal conjugate vaccine), **Group 10)** Flumist Quadrivalent (intranasal influenza live vaccine).

**Arm II: Age 65-80 group:** Groups of 10 study participants ≥65 years of age will be **vaccinated with one of three of the FDA approved vaccines (30 participants total):** **Group 7)** Fluzone intramuscular influenza virus vaccine, **Group 8)** Pneumovax 23, **Group 9)** Prevnar. Meningococcal vaccines, the intradermal influenza vaccine and intranasal Flumist will not be administered to participants in Arm II.

**Arm III: Healthy adults, age 18-80, with a specific medical history as described here and in Section 12.11 (Inclusion Criteria):** Groups of 25 study participants will be vaccinated with the Fluzone intramuscular influenza virus vaccine (100 participants total). **Group 11)** Prior diagnosis of dengue fever or dengue virus infection. **Group 12)** Prior diagnosis of dengue hemorrhagic fever. **Group 13)** Prior diagnosis of chikungunya virus infection. **Group 14)** Prior diagnosis of zika virus infection

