Sample size evaluation was carried out to provide 80% power and 5% of significance for a two-tailed paired t-test to verify pre-post differences in the relative abundance of sugars. For each one of the specific saccharides to be measured, we expect an effect size a 10% change in relative abundance, with a standard deviation of 4.4% - this is based on data presented in Selman et al. (2012). Selman et al. evaluated changes in IgG1 Fc saccharide abundances (galactosylation, fucosylation and sialylation) following influenza vaccination of 10 Caucasian adults. Based on their data, we selected the highest standard deviation, which occurred in abundance of sialylation. Adjustments for error multiplicity were done by a Bonferroni-Correction that reduced the individual significance levels to be 0.017 (0.05 significance divided by 3 sugars evaluated). Another adopted measure for taking into account the uncertainty about the standard deviation was to inflate that estimate by multiplying it by 1.30. This caused our standard deviation to increase to 5.72% from 4.4%. After all described procedures, using the function *n.ttest* in package *samplesize* in R, the initial evaluated sample size resulted in n=7 per group. It is important to emphasize that only samples from subjects with a two-fold increase in vaccine-specific antibody titer will be further analyzed for IgG Fc glycan saccharide composition. Thus, the evaluated sample size was increased to n=10 to accommodate the possibility of having a 20% rate of vaccine non-responsiveness and also the expected rate of volunteer drop-off (10%).

**ARM III:** We have preliminary data on the abundance of afucosylated glycans on anti-dengue envelope protein IgG

from patients with acute dengue virus infection- the data are from one time point (acute infection) and we are comparing two groups: patients with dengue hemorrhagic fever (the severe disease) vs. dengue fever (the mild form of the disease). The maximum coefficient of variation between the two groups was 55%. Assuming that for the present study the populations to be sampled will have the same variability, a sample size of n = 25 (per group) would guarantee 80% power at 5% significance to detect a minimum Fold-Change (FC) of 1.5 (50% increase) when comparing two independent groups with an unpaired two-sided t-test. In this calculation, we are taking into account that 5 pairwise comparisons will be performed, thus the test-wise significance level will be reduced to 0.01.

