**13.9 \* What will be the total number of evaluable participants at all sites over the course of the entire study?**

215

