## 17.0 Recruitment and Advertising

**For assistance consult CRSO to create a robust Recruitment Plan see Help.**

### 17.1 \* What is the plan for recruitment?

**Overview:** The CRROSS will recruit and prescreen 278 volunteers to achieve the enrollment goal of up to 215 volunteers for vaccination. As of the April 2016 amendment, the cohort will include an additional arm containing 100 participants in 4 groups: 25 participants with a history of dengue virus satisfying specific laboratory criteria, 25 additional participants with a history of dengue fever or dengue hemorrhagic fever and specific laboratory findings, 25 volunteers with a history of infection with chikungunya, and 25 volunteers with a history of infection with Zika virus.

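### Arm III vaccinates exactly the 25 per group that its power statement needs, with nothing set aside for non-response or drop-out, and Section 13 reports all 215 enrolled as evaluable

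*Combined protocol and SAP*

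**What the plan says.** - **Section 12.11, first paragraph (the 10-person groups).** A paired t-test calculation gives 7 per group. Glycan composition is then to be measured only in subjects whose vaccine-specific titre at least doubles; no arm is named in that rule. For this reason "the evaluated sample size was increased to n=10 to accommodate the possibility of having a 20% rate of vaccine non-responsiveness", together with an expected 10% drop-out.
- **Section 12.11, Arm III paragraph.** 25 per group is said to give 80% power for a fold-change of 1.5, from a coefficient of variation of 55%, an unpaired two-sided t-test and a test-wise level of 0.01. Losses are not mentioned.
- **Section 12.9, Study Design.** "215 volunteers who meet all the eligibility criteria will be enrolled in this study": 85 in Arm I, 30 in Arm II and 100 in Arm III. For Arm III: "Groups of 25 study participants will be vaccinated with the Fluzone intramuscular influenza virus vaccine (100 participants total").
- **Sections 13.6 and 13.9.** To the 13.6 question "What is the total number of evaluable participants you plan to enroll at Rockefeller University Hospital over the course of the entire study", and to the 13.9 question "What will be the total number of evaluable participants at all sites over the course of the entire study", the answer is 215.
- **Sections 13.7 and 17.1.** 13.7 gives 278 as the number who must sign consent "over the course of the entire study to result in the desired number of evaluable participants". 17.1 says the recruitment office will "recruit and prescreen 278 volunteers to achieve the enrollment goal of up to 215 volunteers for vaccination".

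**The concern.** The first calculation in Section 12.11 treats enrolled and analysable as different numbers and inflates one to reach the other. The Arm III calculation, in the same section, treats them as equal, although the titre rule is worded for all subjects and volunteers in any arm may withdraw. Section 13 then carries the enrolled total forward as the evaluable total. If Arm III loses anyone to either cause, its comparisons run on fewer than the 25 per group on which the stated power rests, and the evaluable count no longer describes the primary glycan analysis.

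**Working it through.** **1. The 215.** Arm I: 6 × 10 + 25 = 85. Arm II: 3 × 10 = 30. Arm III: 4 × 25 = 100. Total 215, so the evaluable figure is enrolment with zero loss.

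**2. The 7 and the 10.** Inputs from 12.11: change 10, SD 4.4 × 1.30 = 5.72, two-sided alpha 0.017. Noncentral-t power for a paired test is 0.742 at n = 6 and 0.862 at n = 7, so 7 reproduces. Then 7 / (0.8 × 0.9) = 9.72, rounded up to 10, also reproduces. The retention this implies is 0.8 × 0.9 = 0.72. (Adding the two losses, 7 / 0.70 = 10, fits equally well.)

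**3. Analysable numbers if those rates apply to Arm III.**
- Both losses: 25 × 0.72 = 18 per group (additive version: 17.5).
- Non-response only: 25 × 0.8 = 20.
- Drop-out only: 25 × 0.9 = 22.5, taken as 22.
- All groups, both losses: 215 × 0.72 = 154.8 (additive: 150.5). With both losses in Arms I and II (115 × 0.72 = 82.8) but drop-out only in Arm III (100 × 0.9 = 90), the total is 172.8.

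**4. Arm III power.** Two-sample noncentral t, 2n − 2 degrees of freedom, noncentrality d√(n/2), two-sided alpha 0.01, fold-change 1.5, CV 55%. The plan does not state the analysis scale, so three are shown:
- raw scale, common SD: d = 0.5 / 0.55 = 0.909
- log scale: d = ln 1.5 / √ln(1 + 0.55²) = 0.405 / 0.514 = 0.789
- raw scale, CV 55% in both groups: d = 0.5 / √((0.55² + 0.825²)/2) = 0.713

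| n per group | raw, common SD | log | raw, constant CV |
|---|---|---|---|
| 25 | 70.1% | 54.6% | 44.4% |
| 22 | 62.5% | 47.5% | 38.1% |
| 20 | 56.9% | 42.5% | 33.8% |
| 18 | 50.7% | 37.3% | 29.5% |

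The loss from 25 to 18 is 15 to 19 points; from 25 to 22 it is 6 to 8. The fold-change detectable with 80% power at 18 per group is 1.66, 1.85 or 2.07; at 25 it is 1.55, 1.67 or 1.80. On the scaling most favourable to the plan (log2 of 1.5 divided by 0.55, d = 1.064), power is 85% at 25, 79% at 22 and 68% at 18.

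**5. Groups not affected.** The 10-person groups expect 10 × 0.72 = 7.2 analysable against the 7 required. Group 2 expects 25 × 0.72 = 18 against the 7 that a paired test requires.

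**6. The 278.** 278 / 215 = 1.29, which might look like an allowance for loss. Section 17.1 places it before vaccination, with at most 215 vaccinated, whereas non-response can arise only after vaccination. Section 12.9 puts telephone prescreening before the consent visit, so 278 prescreened and 278 consented are different counts.

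**The case against.** The documents never define evaluable. Section 13.6 asks how many evaluable participants will be enrolled, and 215 agrees with enrolment throughout. Vaccinated participants who fail the titre rule can still contribute cytokine, cell, gene-expression and safety data. A reader might infer that the evaluable count is overstated by more than a quarter; without a definition that does not follow. What stands is that 215 is not the number expected in the primary glycan analysis.

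The 20% and 10% rates appear only in the paragraph that sizes the 10-person groups. Arm III is followed for 3 weeks rather than 12 and is paid at least $100 per visit, so its drop-out may be lower. A reader might take 18 per group as the plan's own result; it is the low end of a range that depends on borrowed rates. What stands is that the plan gives no Arm III rate, and either loss alone, at the borrowed rates, leaves fewer than 25.

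It is also tempting to set 51%, 37% or 29.5% against the stated 80% and blame the missing allowance for the whole gap. Much of it is present at 25 per group before anyone is lost. Likewise, 278 × 0.72 = 200 does not show that 215 is unreachable, since the plan never intends to vaccinate 278.

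Group 2 should not be called short on its own account. Its number matters here only if it is the uninfected comparator for Arm III. Its matching size suggests this, but 12.11 does not list the five comparisons.

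**Conclusion.** The point holds in this form: Arm III's power statement requires 25 analysable per group, exactly 25 are vaccinated, and no loss is allowed for, although the same section allows for two losses elsewhere. If the rates used for the 10-person groups carry over, 18 to 22 per group are analysable, and the missing allowance costs between 6 and 19 percentage points of power, depending on which losses apply and on the analysis scale. That every loss scenario lowers power does not depend on the scale; the size of the drop does. The shortfall from 80% at the full 25 is a different question and should be settled separately. The 215 in 13.6 and 13.9 is a correct count of those vaccinated, but it is not the analysable count for the primary outcome.

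**What to change.** - **13.6 and 13.9:** give the number expected to be analysable for the primary glycan outcome, with its assumed rates (about 155 of 215 vaccinated if both apply to every group), or keep 215 and label it as vaccinated.
- **12.11, Arm III:** state the expected non-response and drop-out for Arm III, and restate the power or the detectable fold-change at 18 to 22 analysable per group, naming the analysis scale. List the five comparisons, so that it is clear whether Group 2 is one of the groups compared.
- **13.7 and 17.1:** say whether 278 is the number prescreened or the number consented, and give the other figure.

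These are changes of text and arithmetic. They need no added enrolment and no change to the titre rule; removing that rule for Arm III would change the analysis population and is not needed here. The cost is a less favourable stated power for Arm III. For reference, keeping 25 analysable per group with both losses would take 25 / 0.72 = 34.7, so 35 vaccinated per group; correcting the text does not require it.

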**13.9 \* What will be the total number of evaluable participants at all sites over the course of the entire study?**

215

**13.10 Inclusion Criteria**

Please list participant inclusion criteria:

Order Number	Criteria
--------------	----------

1	

Male or Female 18-80 years of age

2	

Healthy volunteers without significant medical problems

3	

Able to give informed consent to participate

4	

Willing to receive a single dose of an FDA-approved vaccine (either the influenza virus, pneumococcal or meningococcal vaccine)

5	Arm III, Group 11: Prior diagnosis of dengue infection or dengue fever.
6	Arm III, Group 12: Prior diagnosis of dengue hemorrhagic fever
7	Arm III, Group 13: Prior diagnosis of chikungunya virus infection.
8	Arm III, Group 14: Prior diagnosis of zika virus infection.

**13.11 Exclusion Criteria**

Please list participant exclusion criteria:

Order Number	Criteria
1	History of seizure disorder for Flumist group participants only.
1	For Flumist participants: Current illness that limits delivery to nasal airway (mild illness, such as diarrhea or mild respiratory infection with or without fever, and local infections do not apply)
1	For Flumist participants: Close contact with person with severely compromised immune system requiring isolation
2	
 
• Egg allergy for influenza vaccine groups
 

3	
 
• Prior allergic reaction to commercial vaccination
 

4	
 
• In the opinion of the investigator, the volunteer is unlikely to comply with the study protocol.
 

5	
 
• Is pregnant or lactating
 

6	
 
• If Guillain-Barre syndrome (GBS) has occurred within 6 weeks of previous influenza vaccination, the influenza vaccination will not be administered
 

7	
 
• Poor venous access
 

8	
 
• Participation in another clinical study of an investigational product currently or within the past 90 days, or expected participation during this study.
 

9	
 
• Any clinically significant abnormality on medical history or physical examination that, in the opinion of the investigator, would preclude participation.
 

10	
 
• Received any vaccine within the last 4 weeks
 

11	
 
• Unable to complete study
 

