**The study will occur in four phases:**

**Phase 1:** Volunteers will be recruited to receive influenza vaccines (Groups 1, 2, 7, 10). Recruitment for Groups 1 and 7 will occur simultaneously and volunteers will be enrolled sequentially - enrollment into Group 1 will be given priority over Group 2 because the intradermal vaccine preparation for the 2012-13 influenza season will expire earlier than the intramuscular preparation (April 2013 vs. June 2013). Volunteers will be recruited to receive the Flumist influenza vaccine (Group 10) beginning fall of 2013.

**Phase 2:** Volunteers will be recruited to receive one of the pneumococcal vaccines (Groups 3, 4, 8, 9)

- these subjects will be recruited simultaneously and will be randomized to receive either the Pneumovax or Prevnar vaccines.

**Phase 3:** Volunteers will be recruited to receive one of the meningococcal vaccines (Groups 5 and 6) - these subjects will be recruited simultaneously and will be randomized to receive either the MPSV4 or Menveo vaccines.

**Phase 4:** Volunteers will be recruited for Arm III of the study to receive the Fluzone intramuscular vaccine (Groups 11-14)

Study participants will not be blinded. During the analysis phase, samples will be coded so that the precise vaccine administered within each phase is unknown.

Study visits will be scheduled as follows for groups 1-10: screening, day 0 (within 4 weeks of screen), day 7 safety visit, and weeks 3, 5, 7, 9, and 12. On Day 3-4, a telephone call will be made to check on subject's medical status.

Groups 11-14 will be scheduled as follows: day 0 (within 4 weeks of screen), day 7 safety visit, and week 3. We will not collect samples at weeks 5, 7, 9 or 12 for Groups 11-14 because our existing data on intramuscular Fluzone immunization from Group 2 demonstrate that the major Fc glycan modifications occur during the first 3 weeks following vaccination.

**We do not anticipate any safety issues related to this protocol as all vaccines to be used have been FDA approved and all study participants are healthy adults.**

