#### **Protocol Timeline**

See Study Design groups 1-10 in other study documents

See Study Design groups 11-14 in other study documents

Subjects in Groups 1 and 2 (Fluzone ID < 65 years of age and Fluzone IM < 65 years of age) will be asked to return to the clinic for an additional study visit between 6 and 12 months from their Day of Vaccination (Day 0). This visit will include vital signs, any updates to their medical/vaccination history, as well as a blood draw of 23.5 ml for sera and PBMCs. The rationale to include this additional timepoint is that our data from subjects who received the 2012-13 Fluzone vaccines show modulations in Fc glycan composition on antigen-specific IgGs post vaccination; the Fc glycans change over time following vaccination, but are not at baseline composition by the 12 week timepoint (the latest timepoint) in our study. Inclusion of the 6-12 month timepoint in the Fluzone study groups will enable better characterization of the kinetics of Fc glycan changes, which is important since the modifications are likely to augment IgG effector functions. We will collect a detailed history of any vaccinations or illnesses occurring since the last study visit in order to incorporate the information into our analysis. Sera collected at this late timepoint will enable analysis of Fc glycan composition and PBMCs will enable analysis of vaccine-specific B and T cell functioning.

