#### **Sample preparation and laboratory analysis**

Leukocytes will be separated from plasma, red blood cells and platelets by Ficoll (GE) gradient centrifugation. Plasma, serum and cells will be frozen for analysis at a later time. The serum will be characterized for cytokines using luminex multiplex assays and ELISAs. Serum will also be used to extract IgGs for analysis by ELISA, western blot and by mass spec for specificity and Fc glycan content. Fc glycans will be analyzed following isolation of antigen-specific IgGs by affinity chromatography. Vaccine preparations or purified proteins/polysaccharides will be coupled to sepharose beads as previously described for extraction of specific serum IgGs (11-14). Fc glycans from antigen-specific IgGs will be isolated by digestion with EndoS enzyme for subsequent mass spec analysis of the Fc glycan (15). Vaccine preparations for research use will be obtained from the RU pharmacy, purified influenza virus antigens will be obtained from the Biodefense and Emerging Infections Research Resources Repository, purified pneumococcal polysaccharides from ATCC. Serum IgGs will also be used in in vitro and in vivo (murine) assays in the laboratory to assess the functional consequence of Fc glycan modifications during infection with influenza viruses or with Streptococcus pneumonia (16-18). Mice humanized for FcgRs will be used for in vivo studies using human IgGs (19). RNA will be extracted from samples collected in PAXgene tubes for analysis related to specific modifications of IgG Fc glycans occurring post-vaccination.

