#### **12.10 \* Data Analysis**

Describe method(s) of data analysis.

In order to find evidence that IgG Fc glycan composition changes from pre- to post-vaccination, we will apply two-sided t-tests and wilcoxon

tests for paired samples with significance fixed at 5% when evaluating change in abundance of specific saccharide units. For each vaccine antigen, we will be comparing pre- (day 0) to post- (day 21) vaccination IgG Fc glycan composition in order to see which vaccines elicit significant saccharide modifications. We will apply the same analysis to data obtained through study of samples taken prior to and at day 21 post influenza virus infection. For the analysis of the time course experiment and comparison across different groups, we are going to use Repeated Measures ANOVA, descriptive graphics and possibly fitted curves that may bring information about changes in time. Depending upon results in humans (Aims 1 and 2), in vivo experiments will be carried out in mice. For this stage, our Biostatistical Core will be consulted about the appropriate design and analysis of the experiments.

**12.11 \* Explain the rationale for the choice of statistical measures and the number of participants proposed for the study, including the power calculations when applicable.**

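### The 4-week vaccine exclusion is shorter than the glycan persistence the plan reports after Fluzone, so Day 0 in the influenza groups is not protected from an earlier same-season influenza vaccine

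*Combined protocol and SAP*

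**What the plan says.** **Eligibility.** Section 13.11, item 10, excludes anyone who "Received any vaccine within the last 4 weeks". It applies to all groups and gives no rationale. Nothing else in sections 13.10 and 13.11 sets a longer window for the study antigen. The 90-day rule in item 8 concerns investigational products in other studies, not routine vaccination.

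**Persistence.** The Protocol Timeline reports that 2012-13 Fluzone recipients showed "modulations in Fc glycan composition on antigen-specific IgGs post vaccination", and that "the Fc glycans change over time following vaccination, but are not at baseline composition by the 12 week timepoint". Twelve weeks was the last observation. A visit at 6 to 12 months was added for Groups 1 and 2 for this reason.

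**Timing of the main change.** When it shortens follow-up for Groups 11 to 14, the plan says that in Group 2 "the major Fc glycan modifications occur during the first 3 weeks following vaccination".

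**Measurement and test.** The assay reads IgG purified against the antigen: "Fc glycans will be analyzed following isolation of antigen-specific IgGs by affinity chromatography". Section 12.10 judges each vaccine by "comparing pre- (day 0) to post- (day 21) vaccination IgG Fc glycan composition".

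**Sample size.** Section 12.11 aims for "80% power and 5% of significance for a two-tailed paired t-test", assuming "a 10% change in relative abundance, with a standard deviation of 4.4" percent. The standard deviation is inflated to 5.72 and alpha is cut to 0.017 for three sugars. The result is 7 per group, raised to 10 for non-response and drop-out. Only subjects with a two-fold titer rise go on to glycan analysis.

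**The concern.** The primary test uses each person's Day 0 sample as the reference. If that sample comes from someone vaccinated against the same influenza strains 5 to 12 weeks before, the plan's own data suggest that it may be partly a post-vaccination sample. The paired difference would then understate the vaccine's effect and vary more between people, because affected and unaffected subjects are mixed. If recent same-season vaccination were unevenly spread, the route, age and Arm III comparisons would also be disturbed, although the documents do not say that it is uneven.

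The situation is plausible. Section 9.6 gives IRB approval on 7 February 2013, and Phase 1 used 2012-13 preparations expiring in April and June 2013. Enrolment therefore opened late in a season in which volunteers could already have been vaccinated. As an illustration, a person entering on 1 March 2013 who was vaccinated between 7 December 2012 and 25 January 2013 would be 5 to 12 weeks out and would pass item 10.

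The plan accepts the principle elsewhere. It repeats pregnancy tests because pregnancy alters Fc glycans, and at the 6 to 12 month visit it collects interval vaccinations for use in the analysis. It states no such use for vaccinations before Day 0.

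**Working it through.** **1. The windows side by side.** The exclusion covers 4 weeks. Reported persistence after Fluzone is at least 12 weeks. The uncovered interval is at least 12 − 4 = 8 weeks. Its end is unknown, because observation stopped at 12 weeks.

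**2. The plan's sample size.** Inputs from section 12.11: change d = 10, SD = 4.4 × 1.30 = 5.72, alpha = 0.05/3 ≈ 0.017, two-sided paired t-test. Power comes from the noncentral t distribution with n − 1 degrees of freedom and noncentrality (d/SD)√n.

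- n = 6: power 74%
- n = 7: noncentrality (10/5.72)√7 = 4.63, power 86%
- n = 10: power 99%

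The smallest n reaching 80% is 7, as stated. Inflation gives 7/(0.8 × 0.9) = 9.7, so 10. The plan's figures reproduce.

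**3. Effect of a displaced baseline.** The documents give no values for two quantities, so both are assumed over a range:

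- p, the share of analysed subjects with a recent same-season influenza vaccine;
- r, the fraction of the 10-point shift still present at Day 0.

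A further assumption is that day 21 reaches the same level whatever the starting point. An affected subject's change is then 10(1 − r).

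- Mean change = 10(1 − p·r)
- SD of change = √[5.72² + p(1 − p)(10r)²]

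At p = 20%:

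| r | Mean change | SD of change |
|---|---|---|
| 0.25 | 9.5 | √(32.7 + 1) = 5.8 |
| 0.50 | 9.0 | √(32.7 + 4) = 6.1 |
| 1.00 | 8.0 | √(32.7 + 16) = 7.0 |

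**4. Power by simulation** (paired t-test, alpha 0.017; using 0.05/3 exactly moves the figures by less than one point). Power with no one affected is 86% for 7 analysed and 99% for 10.

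| Analysed | p | r = 0.25 | r = 0.50 | r = 1.00 |
|---|---|---|---|---|
| 7 | 10% | 84% | 79% | 66% |
| 7 | 20% | 81% | 72% | 48% |
| 7 | 30% | 78% | 65% | 34% |
| 10 | 20% | 97% | 93% | about 72% |

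**5. The larger groups.** Group 2 and Groups 11 to 14 enrol 25 each. On the same inputs, with 20 analysed, p = 20% and full displacement, power for the paired test is still 98.5%. The shift in the mean, 10·p·r points, does not shrink with n.

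**The case against.** **Is this a contradiction?** A reader might infer that the plan contradicts itself. It does not. Item 10 makes no claim that glycans have recovered by 4 weeks, and the 12-week finding came from later data. This is an eligibility window that was not revisited.

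**Does it reach every recent vaccinee?** A reader might infer that anyone vaccinated one to three months earlier has a spoiled baseline. The documents do not support that. The finding concerns antigen-specific IgG after Fluzone, and the assay reads only antigen-specific IgG. Nothing shows that an unrelated vaccine shifts that fraction. Nor does the finding extend to the pneumococcal and meningococcal groups, where whether the vaccine changes glycans at all is part of the study question.

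**Is the residual large?** The major changes are said to fall in the first 3 weeks, and glycans keep changing afterwards. Not being at baseline is not full displacement, so r = 1 is a bound and not an expectation. At a 25% residual, power stays close to the 80% target. This objection stands.

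**Would affected people be analysed?** Some might already have raised titers and fail the two-fold rule. That is an inference, and it stands in part: the rule could remove some bias. It is not a washout, however, and each removal uses up an evaluable subject in a group of 10 sized to leave 7. A free influenza vaccine may also appeal less to people already vaccinated. This too is an inference, and it points to a small share.

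**Is vaccination history already taken?** Screening includes a complete medical history, and the late visit asks for updates to vaccination history, so dates may exist. The text supplied names no dated same-antigen item and no analysis use for one.

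**Are older participants hit harder?** A reader might infer that the 65-and-over groups carry more prior vaccination. The documents say nothing on this.

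**Conclusion.** The point holds for same-antigen influenza vaccination. The 4-week rule does not protect Day 0 over an interval of at least 8 weeks in which the plan's own Fluzone data show glycans still away from baseline, and no other criterion closes that gap. The likely direction is toward no change, provided that day 21 does not depend on the starting level.

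The size cannot be fixed from the documents, because p and r are both assumed. At p = 20% with 7 analysed, power falls from 86% to between 81% (r = 0.25) and 48% (r = 1), with 72% at r = 0.50. With all 10 analysed and r = 0.50 it is 93%. The planned sample size is correctly computed and does not change. This is an inexpensive improvement to the validity of the baseline. It does not show that results already obtained are wrong.

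**What to change.** 1. Reconcile section 13.11, item 10, with the Protocol Timeline. For baseline validity in the influenza groups (1, 2, 7, 10 and 11 to 14), do not enter people who already received the current season's influenza vaccine. Keep the existing 4-week rule for unrelated vaccines.
2. For the pneumococcal and meningococcal groups, have the sponsor justify whatever same-antigen window it adopts. The documents establish no length. The 6-month opening of the late visit is not evidence of recovery, since that visit was added because the time course beyond 12 weeks was unknown.
3. Record the date and type of the last same-antigen vaccine for every participant, retrospectively where possible.
4. Pre-specify a sensitivity analysis of the day 0 to day 21 change that excludes, or adjusts for, recent same-antigen vaccination. Include participants already enrolled, and report how many are affected in each group.

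The cost is one eligibility line, one dated case report form field if none exists, one extra analysis and slightly slower recruitment.
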